1.2 Primary Objectives

- 1.2.1** To evaluate safety and tolerability of administering NeoVax in patients with high-risk melanoma
- 1.2.2** To determine the feasibility of generating and administering NeoVax in patients with high-risk melanoma

Two feasibility endpoints will be evaluated:

- (1) The proportion of patients for whom sequencing and analysis leads to identification of at least 10 actionable peptides to initiate vaccine production
- (2) The proportion of patients for whom the time between surgery and vaccine availability is 12 weeks or less (excluding those patients who did not generate at least 10 actionable peptides)

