5 TREATMENT PLAN

Treatment will be administered on an outpatient basis. Expected toxicities and potential risks as well as dose modifications for NeoVax are described in Section 6 (Expected Toxicities and Dosing Delays/Dose Modification). No investigational or commercial agents or therapies other than those described below may be administered with the intent to treat the patient's malignancy.

Patients with clinically evident locoregional metastatic disease or fully resectable distant metastatic disease as defined in 3.1.3 will be identified and enrolled on the study. After signing consent, the patients will undergo surgery with the intention to remove all melanoma (curative intent). Tissue procurement will be performed as described in 5.1. After confirmation of complete tumor resection by pathologic review and determination of adequacy of DNA and RNA yield from tumor tissue for sequencing, the generation of the vaccine as described in 5.2.1 will be initiated. Patients with tumors that are not completely resected and/or that provide inadequate DNA and/or RNA for sequencing will be removed from the trial and replaced.

CONFIDENTIAL

This document is confidential. Do not disclose or use except as authorized.

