Stopping rule for Expansion Cohort: If four or more patients in the expansion cohort experience dose limiting toxicity (DLT) during the first 7 weeks of treatment, then the dose expansion cohort will be determined to have unacceptable toxicity and the study will be stopped prior to completion of enrollment of the expansion cohort. The table below summarizes the probability of observing 4 or more DLTs within the 10 patients of the expansion cohort for varying underlying rates of toxicity.

Probability of observing 4 or more patients with DLT	True, but unknown, toxicity rate					
	5%	10%	20%	30%	36%	40%
	0.001	0.013	0.121	0.350	0.513	0.618

If the true probability of DLT in the expansion cohort is higher than 35%, then the probability is at least 50% of observing 4 or more patients with DLT within the 10 patients of the expansion cohort.

Total Sample Size: The final sample size for this trial will depend upon the number of dose-escalation cohorts; however, the number of patients enrolled will be between 4 and 20. The minimum number of patients to be enrolled is based on observing DLTs after the first dose of NeoVax in the first two patients of cohort 1 and similarly in cohort-1. The maximum would occur if Cohort 1 and Cohort -1 were enrolled, with an additional 10 patients at the recommended dose.

B: To determine the feasibility of generating and administering NeoVax in patients with high-risk melanoma

Two feasibility endpoints will be evaluated:

- 1) The proportion of patients for whom sequencing and analysis leads to identification of at least 10 actionable peptides to initiate vaccine production;
- 2) The proportion of patients for whom the time between surgery and vaccine availability is 12 weeks or less (excluding those patients who did not generate at least 10 actionable peptides).

We will base the primary assessment of feasibility on all patients enrolled with a confirmation of completely resected tumor and with adequate DNA and RNA for sequencing. The statistical considerations for feasibility that follow are based on 15 patients.

CONFIDENTIAL

This document is confidential. Do not disclose or use except as authorized.

However, the decision rule used to assess feasibility will be adjusted to maintain the operating characteristics if the number of patients is greater than 16.

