We would consider NeoVax to be feasible if no more than 50% of patients have fewer than 10 actionable peptides or have NeoVax available more than 12 weeks after confirmation of complete resection. If 4 or fewer of the first 15 patients have insufficient vaccine or first dose delays of more than 12 weeks, then the upper bound of the one-sided 90% exact confidence interval will be less than 50% and we will consider the process feasible. If 5 or more of the first 15 patients have insufficient or delayed vaccine, we will consider the vaccine not feasible.

The planned vaccination regimen will be administered even if the feasibility endpoints are not met. However, the treatment will not be started in a given patient if three or fewer actionable peptides are identified.

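### The feasibility verdict covers only patients with sequenceable tissue, and no planned result counts completely resected patients replaced for inadequate DNA or RNA.

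*Combined protocol and SAP*

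**What the plan says.** Section 1.2 gives the second primary objective as "To determine the feasibility of generating and administering NeoVax in patients with high-risk melanoma", and Section 14.1, part B, repeats it. The first feasibility endpoint there is "The proportion of patients for whom sequencing and analysis leads to identification of at least 10 actionable peptides to initiate vaccine production". The second is the proportion with vaccine available within 12 weeks.

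The analysis set is narrower than the objective. Section 14.1 restricts the primary assessment to enrolled patients with "completely resected tumor and with adequate DNA and RNA for sequencing". Section 5 says that patients with incompletely resected tumors, or "that provide inadequate DNA and/or RNA for sequencing will be removed from the trial and replaced".

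The decision rule follows in 14.1: "The statistical considerations for feasibility that follow are based on 15 patients". The threshold is a 50% failure rate. Four or fewer failures of 15 is a pass, because "the upper bound of the one-sided 90% exact confidence interval will be less than 50" percent; five or more is not feasible. Failures are patients with insufficient or late vaccine. The rule is to be adjusted if more than 16 patients are assessed.

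Sections 5.1.1 and 5.1.2 allow a tumor cell line, if one was generated, or paraffin-embedded samples as a back-up source of nucleic acid.

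**The concern.** A patient who consents, is registered, has all tumor removed and then yields too little DNA or RNA cannot receive this vaccine. Under Sections 5 and 14.1 that patient appears in neither the numerator nor the denominator, and another patient takes the place. Had the patient been counted, it could only have been as a failure, so the exclusion works in one direction.

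Feasibility is one of two primary goals and ends in a binary statement. A reader told that NeoVax is feasible will take this to apply to the population in the objective, patients with resected high-risk melanoma. The published text of Section 14 plans no result that includes the replaced patients and does not ask for their number. The reader could not tell whether the statement survives when they are counted.

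**Working it through.** **Inputs.** From 14.1: n = 15, failure threshold 50%, one-sided 90% exact bound, pass at 4 or fewer. From Section 5: patients with inadequate DNA or RNA are replaced. Not in the documents: how often tissue is inadequate. It is treated below as an assumed range.

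**Formula.** For x failures in n, the exact one-sided 90% upper bound is the 0.90 quantile of a Beta(x + 1, n − x) distribution. It lies below 50% exactly when P(X ≤ x | n, 0.5) is below 0.10, so each result can be checked by hand.

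**The plan's own rule.**
- 4/15: P = (1 + 15 + 105 + 455 + 1365)/32768 = 0.059; bound 46.4%; feasible.
- 5/15: P = (1941 + 3003)/32768 = 0.151; bound 53.2%; not feasible.

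The rule reproduces. The largest passing count is also 4 at n = 16 and becomes 5 at n = 17, which agrees with adjusting only above 16.

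**Adding back k excluded patients as failures**, so x/15 becomes (x + k)/(15 + k).

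From 4/15, k = 1 gives 5/16: P = (1 + 16 + 120 + 560 + 1820 + 4368)/65536 = 6885/65536 = 0.105; bound 50.35%; not feasible. The plan's own cut-off of 4 at n = 16 gives the same answer. Two added give 6/17, bound 53.7%; three give 7/18, bound 56.7%.

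From 3/15, one added gives 4/16 (43.9%) and two give 5/17 (47.8%), both still feasible. Three give 6/18: P = 0.119; bound 51.2%; not feasible.

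Smallest k that reverses a pass:

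| Result in primary set | k needed | Result with k added | Upper bound |
|---|---|---|---|
| 4/15 | 1 | 5/16 | 50.4% |
| 3/15 | 3 | 6/18 | 51.2% |
| 2/15 | 5 | 7/20 | 51.8% |
| 1/15 | 7 | 8/22 | 52.3% |
| 0/15 | 8 | 8/23 | 50.3% |

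**Effect on the error rate, under assumptions.** Suppose the true failure rate over all completely resected enrolled patients is 50%, and a share d of them have inadequate DNA or RNA. The failure rate inside the primary set is then q = 1 − 0.5/(1 − d), and the chance of a feasible verdict is P(X ≤ 4 | 15, q).

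| Assumed d | q | Chance of a feasible verdict |
|---|---|---|
| 0% | 0.500 | 5.9% |
| 5% | 0.474 | 8.7% |
| 10% | 0.444 | 12.9% |
| 15% | 0.412 | 19.1% |
| 20% | 0.375 | 28.0% |
| 25% | 0.333 | 40.4% |
| 30% | 0.286 | 56.5% |

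For this wider population, the nominal 10% error is passed somewhere between 5% and 10% inadequacy.

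**The case against.** The strongest defence is that the plan draws its boundary on purpose and in the open. Section 5, and footnote 11 of the study calendar in Section 9, both start vaccine preparation only after the specimen is judged adequate. On that wording inadequate tissue is a failed entry condition, like incomplete resection. The opening of 14.1 states the goal as making a vaccine with enough actionable peptides in good time, which fits the restricted set, and the assessment is labelled primary. Patients with adequate nucleic acid but fewer than 10 peptides still count as failures. This stands: the set is a legitimate estimand, and there is no reason to replace it. It does not answer why the wider objective has no accompanying result.

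The size is also uncertain. The back-up sources will rescue some patients, and at an assumed 5% inadequacy the error stays within the nominal 10%. That stands too. The back-up does not remove the problem, because a cell line may not exist and Section 5 keeps the replacement rule.

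The consequence is limited. Section 14.1 says that vaccination continues even if the feasibility endpoints are not met, so the point affects what is reported and not any patient's treatment.

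**Conclusion.** The point holds as a matter of scope. The feasibility verdict is conditional on sequenceable tissue, the objective is not, and the difference can only favour a pass. Counting one excluded patient reverses the verdict at exactly 4/15, and narrowly (50.35% against 50%). At 3/15 it takes three, and at 0/15 eight. These counts treat each excluded patient as a failure and use the plan's own bound. The error rates rest further on an assumed inadequacy rate and an assumed 50% true failure rate.

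Two stronger readings are not supported. A reader might infer that a single excluded patient generally overturns the conclusion; the calculation shows this at one boundary result only. A reader might also infer that the rule is miscalculated or the exclusion hidden; the rule reproduces exactly and both exclusion and replacement are written down. Nor do the documents show that inadequate tissue will be common. This is a cheap improvement, not the repair of an error.

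**What to change.** Keep the stated primary set and add one pre-specified sensitivity result to 14.1:

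- Population: all enrolled patients with confirmed complete resection. Those whose DNA or RNA is still inadequate after the back-up sources in 5.1.2 count as failures. Incompletely resected patients stay out, since that is a clinical eligibility matter.
- Method: the same exact one-sided 90% bound against 50%, with the cut-off re-derived for the actual n (4 at n = 15 or 16, 5 at 17 or 18, 6 at 19 or 20).
- Reporting: the number replaced for inadequate DNA or RNA, and whether the feasibility conclusion changes. If it does, word the conclusion as applying to patients with sequenceable tissue.

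A proportion of all initially registered patients who started vaccination on time is not a good substitute. It would mix in incomplete resection, failure of secondary eligibility and withdrawal, and it would need a definition of on time.

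The cost is a few lines in 14.1 and a table row. Registration precedes surgery, so these patients are already identified. Section 4.1 calls for cancelling registrations that do not lead to study therapy, so the text should say that the reason is retained. The downside is that the reported feasibility figure may be less favourable.

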5.4.2 Staggering of patients in DLT cohorts

5.4.3 The first three patients of Cohort 1 and Cohort -1 will be enrolled in a staggered fashion: Patients 2, 3 and 4 will not start treatment until the week after the previous

CONFIDENTIAL

This document is confidential. Do not disclose or use except as authorized.

patient has completed the priming phase (scheduled for day 22). **Prime/boost schedule**

Vaccine will be administered following a prime/boost schedule. Priming doses of vaccine will be administered on days 1, 4, 8, 15, and 22 as shown above (Section 5.3, Administration and Schema B). In the boost phase, vaccine will be administered on days 78 (week 12) and 134 (week 20).

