¹⁰Resection of locoregional metastatic disease (regional lymph nodes, in transit metastases, satellite lesions, limited distant metastases) and primary tumor (if not yet removed) should occur within 3 weeks of study enrollment.

¹¹Vaccine preparation should begin immediately after the surgical specimen is deemed adequate for vaccine preparation and it has been determined that the primary melanoma and metastatic disease have been completely removed. Vaccine preparation should be completed within 8-10 weeks after this assessment.

¹²Patients will undergo leukapheresis procedure to collect sufficient amounts of PBMCs to allow comprehensive immune monitoring. The pre-treatment leukapheresis should be performed no sooner than 2 weeks after the surgery, prior to the first vaccine administration. A +/- 7 day window is allowed for the day 106 leukapheresis. If a patient is discontinued from active treatment (during Priming or Boosting Phase) and has not yet undergone the day 106 leukapheresis, the leukapheresis or a 50 ml blood draw should be performed no later than 14 days after the day of discontinuation.

¹³135 ml of blood should be drawn if pre-treatment leukapheresis cannot be performed. If pre treatment Leukapheresis was performed 20 ml should be drawn.

¹⁴If pre-treatment leukapheresis cannot be performed, there is no blood draw. If leukapheresis was performed, 60 ml of blood will be collected.

¹⁵200 ml

¹⁶200 ml of blood should be drawn if week-16 leukapheresis cannot be performed. If week -16 leukapheresis can be performed, there is no blood draw.

¹⁷ Follow-up: Every 3 months re-staging follow-up visits (+/- 1 week) should continue until initiation of a new therapy for recurrent disease, withdrawal of consent, or death whichever occurs first for a total of 2 years after treatment initiation.

¹⁸ Every 6 months

¹⁹ Assessments such as: Medical History / Physical Examination, lab tests and Con Meds can be done on Day 1 visit (previous starting treatment) if needed

CONFIDENTIAL

This document is confidential. Do not disclose or use except as authorized.

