Five patients will be entered for the initial safety evaluation (Cohort 1). We have chosen dose escalation cohorts of 5 patients, rather than a more traditional 3+3 design, because the determination of whether to treat at a different dose in this trial is made over a longer period of time due to the staggered enrollment of patients, the time required for vaccine preparation, and the extended period for safety evaluation. These larger cohort sizes help us avoid having to pause and then restart enrollment to a dosing cohort several months later. If two or more patients in Cohort 1 experience dose limiting toxicity (DLT) during the first 7 weeks of treatment, then that cohort will be determined to have unacceptable toxicity; otherwise, an additional 10 patients will be treated at this dose level to increase the likelihood of detecting serious toxicities, to complete biologic correlative endpoints, and to gain preliminary experience with clinical tumor activity. If Cohort 1 is found to have unacceptable toxicity, then 5 patients will be enrolled on Cohort -1. If two or more patients in Cohort -1 experience a DLT, then the study will be stopped. If zero or one patient experiences a DLT in Cohort -1, then 10 additional patients will be enrolled in an expansion cohort.

The table below shows the probability of moving to the dose expansion phase (0 or 1 patients with DLT out of 5 patients) for various possible values of the true, but unknown, toxicity rate.

True rate of DLT (%)	Probability of Dose Expansion (%)
10	92
20	74
30	53
40	34
50	19
60	9

If the true probability of DLT is 10% or less, then the probability of proceeding to dose expansion is at least 92%. The probability of dose expansion is less than 50% if the true rate of dose-limiting toxicities is 32% or greater.

Minimum vaccination requirement to pass DLT observation period: A minimum of 3 vaccinations and absence of DLTs are required for a patient to complete the 7-week DLT observation period successfully.

Expansion Cohort: When the recommended dose has been determined, an expansion cohort of 10 patients will be enrolled to assess the performance of the vaccine and to gain additional information about toxicities.

CONFIDENTIAL

This document is confidential. Do not disclose or use except as authorized.

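### The feasibility pass clause counts late first doses while the endpoint and the fail clause concern late vaccine, so the two clauses need not be complementary

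*Combined protocol and SAP*

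**What the plan says.** Sections 1.2.2 and 14.1 part B define feasibility endpoint 2 in the same words: "The proportion of patients for whom the time between surgery and vaccine availability is 12 weeks or less", leaving out patients without at least 10 actionable peptides.

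The decision rule follows in section 14.1 part B, in three consecutive sentences:

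- The definition of feasible tolerates at most 50% of patients who have fewer than 10 actionable peptides or "have NeoVax available more than 12 weeks after confirmation of complete resection".
- The pass clause reads "If 4 or fewer of the first 15 patients have insufficient vaccine or first dose delays of more than 12 weeks"; the one-sided 90% exact upper bound is then below 50% and the process is called feasible.
- The fail clause reads "If 5 or more of the first 15 patients have insufficient or delayed vaccine, we will consider the vaccine not feasible".

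Three other places bear on this:

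- Section 5.4.2/5.4.3 staggers the start of the DLT cohorts: "Patients 2, 3 and 4 will not start treatment until the week after the previous" patient has finished priming, scheduled for day 22.
- Section 9, footnote 11, gives the production time, counted from the finding that the specimen is adequate and the resection complete: "Vaccine preparation should be completed within 8-10 weeks after this assessment".
- Section 14.1 part A explains the five-patient cohorts by a dose decision "made over a longer period of time due to the staggered enrollment of patients".

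**The concern.** Vaccine availability and first dose are separate events in this trial. Peptides are stored frozen (section 7.2.3) and mixed with poly-ICLC on the day of dosing (section 7.2.7), so a finished vaccine can wait. The protocol itself imposes a wait on patients 2, 3 and 4.

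Take a patient whose vaccine is ready at week 10 and whose first dose falls at week 13 because the previous patient is still in priming. That patient meets endpoint 2. Under the literal pass clause the same patient is a failure. Under the fail clause the vaccine was not late, so the patient is probably not a failure. No text says that safety or medical waits are left out, or that a late first dose is shorthand for a late vaccine.

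The start of the clock also varies: surgery in endpoint 2, confirmation of complete resection in the definition of feasible, and nothing in the pass clause.

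At stake is the conclusion on a primary objective. Only 4 failures in 15 are allowed, so reclassifying one or two patients can reverse it, and the choice of reading would be made after the data are known.

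**Working it through.** **1. The plan's own figure.** The one-sided 90% exact upper bound for x failures in 15 is the 0.90 quantile of Beta(x+1, 15−x).

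- x = 4: 0.464, with P(X ≤ 4 | p = 0.5) = 0.059.
- x = 5: 0.532, with P(X ≤ 5 | p = 0.5) = 0.151.

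The limit of 4 in 15 reproduces. Only the classification of patients is in question.

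**2. The clauses side by side.**

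| Place | Event counted | Clock starts at |
|---|---|---|
| Endpoint 2 (1.2.2, 14.1 B) | vaccine availability | surgery |
| Definition of feasible (14.1 B) | vaccine availability | confirmation of complete resection |
| Pass clause (14.1 B) | first dose | not stated |
| Fail clause (14.1 B) | delayed vaccine | not stated |

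As an illustration, suppose 3 patients have late vaccine and 2 have on-time vaccine with a first dose held past week 12. Then 3 + 2 = 5 patients count against passing, so the pass clause is not met. Only 3 clearly count towards failing, so the fail clause is not met either.

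**3. How many first doses the stagger alone could push past week 12.** Inputs:

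- T, vaccine ready: 56 or 70 days (8 or 10 weeks, section 9, footnote 11), with the 12-week clock assumed to start at confirmation of resection.
- Limit: 84 days.
- g, step between consecutive first doses: 22 to 28 days (my reading of the week after day 22).
- s, days between resections: not given, so shown as a range with even spacing.

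Every vaccine is assumed ready on time, and the stagger is assumed to run within this trial alone. Patient k (k = 2, 3, 4) waits (k−1) × max(0, g−s) days and is late if T + wait > 84.

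For example, with T = 70 and s = 14:

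- g = 22: waits of 8, 16 and 24 days give first doses at days 78, 86 and 94, so 2 are late.
- g = 28: waits of 14, 28 and 42 days give days 84, 98 and 112, again 2 late.

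| Spacing s | Late first doses, T = 70 | Late first doses, T = 56 |
|---|---|---|
| 7 days | 3 | 2 |
| 14 days | 2 | 0–1 |
| 21 days | 0–1 | 0 |
| 28 days | 0 | 0 |

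Where a range is shown, the lower value is for g = 22 and the upper for g = 28.

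**4. Effect on the conclusion.** If m patients are scored as failures only because of the hold, and each of the others fails independently with probability q, then P(declared feasible) = P(Bin(15−m, q) ≤ 4−m). The plan gives no value for q, so it is an assumption.

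| q | m = 0 | m = 1 | m = 2 | m = 3 |
|---|---|---|---|---|
| 10% | 0.987 | 0.956 | 0.866 | 0.659 |
| 20% | 0.836 | 0.698 | 0.502 | 0.275 |
| 30% | 0.515 | 0.355 | 0.202 | 0.085 |

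**5. Effect of the clock.** With preparation taking 70 days from confirmation, the vaccine is on time on the confirmation clock. On the surgery clock it is late once 70 + d > 84, that is, when confirmation comes d ≥ 15 days after surgery. The plan does not give d.

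**The case against.** The strongest reply is that the literal reading is the least natural one. Endpoint 2 is defined twice as availability, the sentences on either side of the pass clause speak of the vaccine, and 4 or fewer against 5 or more is plainly meant as one count split in two. A strict 12-week limit on first doses would also sit badly with section 4, which expects first doses 10 to 17 weeks from registration. With surgery within 3 weeks of enrolment (section 9, footnote 10), the upper end is at least 17 − 3 = 14 weeks after surgery. This stands as evidence of intent, but the rule does not say it.

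The second reply is that the stagger may cost nothing. Section 5.4.2/5.4.3 and section 14.1 part A speak of staggered enrolment, and registration precedes surgery, so surgeries may be spaced to match. Pooling the first patients with the parallel glioblastoma trial (section 1.1) could also lower the counts. This stands too.

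Third, the objective covers administering as well as generating NeoVax, so time to first dose is of some interest. That supports reporting it, but endpoint 2 as defined does not measure it.

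A reader might infer from the table that three held patients is an upper limit. The documents do not support that. Cohort −1 has its own stagger, section 1.1 holds later patients until five pooled patients clear the DLT window, day 22 has a window of ±3 days, and section 6.3.1 allows toxicity delays of up to 14 days. None of these is modelled.

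**Conclusion.** The concern holds as a conflict of wording in the decision rule for a primary objective. The pass clause counts a different event from endpoint 2 and the fail clause, and the start date is not uniform. Read literally, the pass and fail clauses need not be complementary.

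The size is conditional. Under the assumptions above, the stagger accounts for anything from no patients to 3. At a 10% true failure rate, 1 to 3 such patients reduce the chance of declaring feasibility from 0.987 to 0.956–0.659.

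Three stronger readings are not supported:

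- That the stagger will make the trial fail on feasibility. Accrual is not given, and the effect may be zero.
- That the cut-off is wrong. It reproduces.
- That patients' treatment is affected. Section 14.1 part B gives the regimen even if the feasibility endpoints are not met.

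The clarification should still be made before the feasibility data are read.

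**What to change.** In section 14.1 part B, have both the pass and the fail clause count patients with fewer than 10 actionable peptides, or with vaccine not available within 12 weeks of the chosen start date. Use that same start date in the definition of feasible and in endpoint 2.

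Surgery is the default because it is the defined endpoint in sections 1.2.2 and 14.1. Its small downside is that it is stricter than confirmation of resection by the length of the pathology interval. The sponsor may prefer confirmation; endpoint 2 should then be changed to match in both sections.

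Report time to first dose descriptively, with the reason for any wait.

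The cost is a few phrases in section 14.1 part B, plus one in section 1.2.2 if confirmation is chosen. The limit of 4 in 15, the sample size, the stagger and the DLT rules do not change.
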